### For Patients with Non-Measurable Disease

Non-Target Lesions	New Lesions	Overall Response
CR	No	CR
Non-CR/Non-PD	No	Non-CR/Non-PD
Not all evaluated	No	Not evaluated
Unequivocal PD	Yes or No	PD
Any	Yes	PD

\* ‘Non-CR/non-PD’ is preferred over ‘stable disease’ for non-target disease since SD is increasingly used as an endpoint for assessment of efficacy in some trials so to assign this category when no lesions can be measured is not advised

#### 6.1.4.4 Duration of Response

Duration of overall response: The duration of overall response is measured from the time measurement criteria are met for CR or PR (whichever is first recorded) until the first date that recurrent or progressive disease is objectively documented (taking as reference for progressive disease the smallest measurements recorded since the treatment started).

The duration of overall CR is measured from the time measurement criteria are first met for CR until the first date that progressive disease is objectively documented.

Duration of stable disease: Stable disease is measured from the start of the treatment until the criteria for progression are met, taking as reference the

smallest measurements recorded since the treatment started, including the baseline measurements.

## **6.2 Other Measures of Effect**

### **6.2.1 N0 nodal control**

The N0 nodal volumes will be defined prior to initiation of the radiation treatment regimen by PET scan and contrast enhanced CT and MR scans performed as part of the pre-study assessments. N0 control will be assessed by weekly physical exams performed during treatment and CT scan of the neck performed at 4- 6 weeks and annually post-treatment. Patients with observed involvement of any of the N0 nodes at any post-treatment interval will be considered to have an N0 failure.

### **6.2.2 Progression-Free Survival**

Progression-Free Survival (PFS) is defined as the duration of time from start of treatment to time of recurrence/progression or death from any cause, whichever occurs first. Progression will be measured as defined by the RECIST criteria (Section 6.1). Patients who do not experience an event (recurrence/progression or death) will be censored at date of last contact.

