**Table 2: Follow-Up Assessments**

	Months  following last IMRT									
	3	6	9	12	15	18	21	24	30	36
Contrast enhanced CT (or MR) or PET CT	X 			X				X		X
QOL questionnaires 	X	X	X	X	X	X	X	X	X	X
History	X	X	X	X	X	X	X	X	X	X
Physical Exam 	X	X	X	X	X	X	X	X	X	X
Vital Signs (BP, HR, temp)	X	X	X	X	X	X	X	X	X	X
Zubrod Performance Status	X	X	X	X	X	X	X	X	X	X
Toxicity Assessments 	X	X	X	X	X	X	X	X	X	X
Disease status 	X	X	X	X	X	X	X	X	X	X

 Must be performed within 28 days of initiation of study treatment, unless a different timeframe is specified

 Assessments should be conducted between 4-6 weeks following the last IMRT treatment

 Includes height and body surface area (BSA); height is collected at pre-study visit only

 p16 expression for eligibility must be detected by immunohistochemistry and in situ hybridization (HPV)

 Must be performed within 8 weeks of start of treatment for cancer

 WOCBP must have a negative serum pregnancy test at least 14 days prior to initiation of cancer treatment

 Acute AEs will be collected up to 90 days following the last IMRT; late radiation toxicities will be collected from 3 months up to 3 years following the last IMRT

 Disease status should be assessed at each follow-up, using RECIST criteria

 Assessments should be performed  $\pm$  2 weeks from date

The imaging assessments at 3 months post-IMRT are optional.

 May be completed by mail if patient is not scheduled for or misses a clinic visit

 Follow-up physical exams may include a flexible fiberoptic nasolaryngoscopy

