## 5.4 Post-Treatment/Follow-up Assessments

The below follow-up evaluations should be performed at the intervals specified in Table 2 following the last IMRT:

- Contrast enhanced CT (or MR) or PET CT should be performed every 12 months to assess for disease progression
- The following should be performed each time a patient is seen in clinic, per standard care (approximately every 3 months for 2 years, every 6 months in year 3). If a clinic visit is missed, then these assessments should be performed at the next visit:
  - History and Physical (including performance status)
  - Vital signs
  - Performance Status
  - Disease status
  - Acute and late toxicity assessments
- QOL questionnaires should be performed at clinic visits. If no clinic visit is scheduled it can be completed by mail and reviewed with the patient at the next clinic visit.
- Acute toxicity assessments should be performed to collect signs of radiation toxicity which occur up to 90 days following the last IMRT with grading per version 4 CTCAE.
- Late radiation toxicity (effects that occur after 90 days following completion of IMRT) will be evaluated at the time points shown in Table 2: Follow-up Assessments (every 3 months until 24 months after completion of IMRT and then every 6 months from 24-36 months after completion of IMRT). Late Toxicity will be scored per version 4 CTCAE.

In addition, if a patient has an unresolved adverse event at the end of study treatment, the event should be followed every 4-6 weeks until it has resolved, returned to baseline or is deemed irreversible, whichever is longer.

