### **6.2.3 Locoregional recurrence-free survival**

Locoregional recurrence-free survival, or locoregional control, is defined as the duration of time from start of treatment to time of recurrence in either the primary tumor or the nodal regions. Patients who do not experience an event will be censored at date of last contact.

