## **7.2 Sample Size and Accrual**

We know of no detailed published data for the primary and secondary endpoints for the study specific p16+/HPV+ OP-SCCA patient population of interest. However, the ‘historical’ data from sixty patients (updated since publication) treated at UVA provides us with a reliable source to guide sample size determination and monitoring guidelines. For those sixty patients, N0 recurrence occurred in 1/60=1.7% and locoregional failure occurred in 6/60=10% with the upper limit of a one-sided 95% CI being 7.7% and 19%, respectively. Three-year PFS from start of radiation treatment is 80% (95% CI (67, 88%)). For sample determination, these estimates will be used to define the null and alternative 3-

year PFS rates. Specifically, we would like to be able to differentiate between a null 3-year PFS rate of 80% versus the alternative of 67%. Assuming uniform accrual of 15 eligible patients a year for 3 years, a minimum follow-up time of 3 years, PFS is exponentially distributed, a one-sided 10% level test then accrual of 45 eligible patients provides approximately 89% power at the alternative. If the exponential assumption is not supported by the data then accrual of 45 eligible patients results in 80% power to test for a decrease of 14% in 3-year PFS with a one-sided 10% exact binomial level test.

A sequential probability ratio test (SPRT) based upon a binomial test of proportions for N0 control rates will be used. Only the upper boundary will be used for monitoring to protect against excessive failures. The stopping boundary are for a SPRT contrasting a 2% versus 8% N0 control rate, with nominal type I and II errors of 10% and 10%, respectively. The slope of the parallel lines for monitoring is 0.043 and the intercepts are 1.516 and 1.516.

Stopping guideline for N0 Failure	
Number of participants	Boundary
2-9	$\geq 2$
10-33	$\geq 3$
34-45	$\geq 4$

For estimation of locoregional control, a sample size of 45 eligible patients produces a two-sided 90% confidence interval with a width equal to 0.17 when the sample proportion is assumed at the observed historical rate of 10%.

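### PFS and locoregional recurrence-free survival are censored at an undefined last contact, not at the last disease assessment, so both may be overstated if patients leave clinic but stay reachable

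*Combined protocol and SAP*

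**What the plan says.** **Censoring.** Section 6.2.2 runs PFS from start of treatment to recurrence, progression (by RECIST) or death from any cause, and adds: "Patients who do not experience an event (recurrence/progression or death) will be censored at date of last contact". Section 6.2.3, on locoregional recurrence-free survival, has the parallel sentence: "Patients who do not experience an event will be censored at date of last contact". Its events are recurrences at the primary or in the nodes; death is not listed. Neither section defines contact.

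**Contact without assessment.** The footnote on quality-of-life forms in Table 2 (Section 5.1) reads: "May be completed by mail if patient is not scheduled for or misses a clinic visit". Section 5.4 says: "If no clinic visit is scheduled it can be completed by mail and reviewed with the patient at the next clinic visit". Section 6.2.5 allows completion in person or by mail without attaching a condition. Section 4.7 asks every patient for these forms into the third year, however long therapy lasted.

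**Disease assessment.** Table 2 schedules visits at months 3 to 24 every 3 months, then at 30 and 36, with the footnote: "Disease status should be assessed at each follow-up, using RECIST criteria". For missed visits, Section 5.4 says: "If a clinic visit is missed, then these assessments should be performed at the next visit". On imaging, it says: "Contrast enhanced CT (or MR) or PET CT should be performed every 12 months to assess for disease progression".

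**Use of PFS.** Section 7.2 sizes the trial to "differentiate between a null 3-year PFS rate of 80% versus the alternative of 67" per cent. Section 7.3 plans Kaplan-Meier estimates and a test of the exponential rate, 0.0744 against 0.1335.

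**The concern.** Progression is established by examination or imaging. Under a last-contact rule, a patient who no longer attends but is still heard from stays in the Kaplan-Meier risk set, and adds person-time to the exponential rate, over a period in which progression could not have been recorded. An unseen progression in that period can only raise the estimate.

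That is the unhelpful direction here, because the PFS test looks for a fall after dose reduction. PFS is a secondary endpoint but it sets the sample size. Locoregional recurrence-free survival is more exposed in one respect: since death is not an event there, a later death cannot bring an unseen recurrence into the count.

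**Working it through.** **1. The plan's own rates.** With exponential PFS, λ = −ln(S)/3.
- S = 0.80: 0.2231/3 = 0.0744.
- S = 0.67: 0.4005/3 = 0.1335.

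Both match Section 7.3.

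**2. Assumptions, none of them in the documents.** A share q of patients leaves clinic permanently at a time U, uniform over 0 to 3 years. They stay in contact to 3 years, and progressions after U are never recorded. A fraction f of first PFS events are deaths, which are always known; f is taken as 0 to 0.3. Leaving is unrelated to progression.

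**3. Overstatement under last contact.** Nobody is then censored before 3 years, so the Kaplan-Meier value at 3 years is one minus the observed event proportion. The overstatement is

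q × (1 − f) × D, where D = P(U < T ≤ 3) = (1 − S)/(3λ) − S.

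- Null: D = 0.20/0.2231 − 0.80 = 0.8963 − 0.80 = 0.0963.
- Alternative: D = 0.33/0.4005 − 0.67 = 0.8240 − 0.67 = 0.1540.

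Percentage points, from f = 0.3 to f = 0:

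| Share q | True PFS 80% | True PFS 67% |
|---|---|---|
| 0% | 0 | 0 |
| 5% | 0.3 to 0.5 | 0.5 to 0.8 |
| 10% | 0.7 to 1.0 | 1.1 to 1.5 |
| 20% | 1.3 to 1.9 | 2.2 to 3.1 |

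For example, q = 10%, f = 0 at the alternative gives 0.10 × 0.1540 = 1.5 points, so 67% reads as about 68.5%. In a trial of 45 that is 45 × 0.10 × 0.1540 = 0.7 missed progressions on average, each worth 1/45 = 2.2 points.

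**4. Sensitivity.**
- With departure uniform over 0.25 to 2.5 years, D becomes 0.1038 and 0.1654. The top of the range is 0.8 points at 5%, 1.7 at 10% and 3.3 at 20%.
- A simulation that also allowed front-loaded failures had 67% reading as 67.8 to 68.5% at q = 10% and 68.7 to 70.1% at q = 20%.

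**5. Exponential rate.** In 2,000,000 simulated patients with f = 0 and follow-up ended at 3 years, q = 10% lowers the estimated rate from 0.0744 to 0.0705 at the null and from 0.1335 to 0.1263 at the alternative.

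**6. With the fix.** Censoring the same simulated patients at U returns the Kaplan-Meier value to 80% and 67%, and the rates to 0.074 and 0.133, within simulation error. This relies on leaving being unrelated to progression.

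**The case against.** **No text says a mailed form sets the censoring date.** This is correct. A reader might infer that PFS is definitely overstated because questionnaires count as contact. The documents neither say that nor rule it out, so only a possible bias is supported.

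**The schedule already guards against this.** Disease status is due at every follow-up visit, missed assessments are made up at the next one, and mailed forms are to be reviewed there. A patient who returns has a progression recorded late, not lost. This stands. The bias needs permanent departure, continued contact and a progression that is never learned of. A death after an unseen progression is still a PFS event, and the calculation gives no credit for it, so for a given share the PFS figures lean high. Annual imaging adds little to the argument, since examinations are more frequent and the scan interval is a separate matter.

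**Does the bias always favour the regimen over the historical result?** A reader might infer so. Section 7.2 does not say how the historical 80% was censored. If last contact was used there too, part of the bias is shared. The supported statement concerns the trial's own estimate only.

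**Does the rule cost power that the fix would restore?** This is tempting for the fallback exact binomial test of 80% against 67%. With 45 patients it rejects at 13 or more failures and has 77% power; unseen progressions at shares of 10 to 20% bring that to about 62 to 72%. But a binomial proportion has no censoring date. Setting the same patients aside as unevaluable gives 71% with 40 patients and 68% with 36. Restored power is not shown, so no power loss is claimed.

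**Conclusion.** The point holds as a conditional one. The censoring date in Sections 6.2.2 and 6.2.3 is not tied to a disease assessment, while the plan provides for contact without one. If some patients leave clinic for good and stay reachable, both endpoints may look better than they are.

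Rounded, the overstatement of 3-year PFS is under 1 point at a 5% share, about 1 to 1.5 points at 10% and about 1.5 to 3 points at 20%, against a planned difference of 80 − 67 = 13 points. With no such patients it is nil. The shares are assumptions; the documents give neither a dropout rate nor a mail-only rate. The primary endpoint, N0 nodal control, is defined as a proportion and is not governed by this censoring sentence.

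This is a cheap improvement, not a flaw that undermines the trial.

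**What to change.** In Sections 6.2.2 and 6.2.3, replace the censoring sentence so that event-free patients are censored at the date of their last disease-status assessment, by examination or imaging, without progression (6.2.2) or locoregional recurrence (6.2.3). Keep death from any cause as a PFS event, as already defined. Use last contact for overall survival only.

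The cost is one sentence in each section. Disease status is already scheduled at each visit in Table 2, so no new data are needed. There are two downsides: slightly less follow-up time is counted, and the estimate is unbiased only if leaving clinic is unrelated to progression. Reporting how many patients have a last contact later than their last assessment, and by how long, would show whether the issue arose.

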### **6.2.3 Locoregional recurrence-free survival**

Locoregional recurrence-free survival, or locoregional control, is defined as the duration of time from start of treatment to time of recurrence in either the primary tumor or the nodal regions. Patients who do not experience an event will be censored at date of last contact.

### **6.2.4 Dose Volume Histograms**

Dose volume histograms will be used to evaluate the difference in radiation dose to critical structures with the decreased dose regimen compared to what the organs would have received if the PTV2 received 50 Gy. DVHs will be prepared from the mean, max, minimum doses to structures, as well as volumes of particular structures receiving certain doses for comparison.

### **6.2.5 Quality of Life Questionnaires**

All patients entered on study will complete the quality of life (QOL) questionnaires at the pre-study assessment and every 3 months for the first year (starting at 6 months post-IMRT), every 6 months for the second and third years. These can be completed in person during a routine scheduled clinic visit or by mail. The QOL questionnaires to be completed are:

1. MD Anderson Symptom Inventory – Head & Neck (MDASI-HN)

2. MD Anderson Dysphagia Inventory (MDADI)
3. Voice Handicap Index-10 (VH-10)

For the MDASI-HN and VH-10, the patient provides a numerical response to each question. For the MDADI, the patient provides one of the following answers to each statement: strongly agree, agree, no opinion, disagree, strongly disagree. The responses provided on each questionnaire at each interval will be tabulated and summarized and post-treatment responses compared to pre-treatment values.

### **6.3 Toxicity and Safety**

Patients will be evaluated for toxicity and safety weekly during radiation treatments (Section 5.1). Adverse events and other symptoms will be graded according to the National Cancer Institute (NCI) Common Terminology Criteria for Adverse Events (CTCAE) Version 4.0. See Section 8 for more details.

The following additional endpoints for toxicity will also be assessed at the toxicity assessments:

1. Grade of acute radiation dermatitis and late subcutaneous fibrosis (stratified by neck dissection or no neck dissection) in the N0 volumes
2. Late radiation toxicity (events that persist or occur after 90 days of completion of IMRT)
3. Neck dissection complication rate (wound breakdown)
4. Grade of xerostomia
5. Grade of dysphagia
6. Acute and late grade 3 or higher adverse event
7. Rate of PEG dependence at 6 months post-IMRT

## **7 STATISTICAL CONSIDERATIONS**

This is a single institution, single arm phase II trial to estimate the efficacy and safety of reduced intensity modulated radiation therapy (39.6 Gy to the clinically uninvolved cervical lymph nodes in the neck) in patients with p16+ oropharyngeal squamous cell carcinoma. Specifically, the study is designed to estimate N0 nodal control and locoregional control rates, to estimate 3-year progression-free survival, and to define the safety profile of the treatment regimen to determine if the data support further research.

### **7.1 Study Design/Endpoints**

Estimation and safety monitoring for N0 nodal control, locoregional control and 3-year progression-free survival guided sample size determination and monitoring

rules. Data from sixty p16+ OP-SCCA patients treated with standard IMRT at UVA from 2002-2011 with adequate follow-up were used to define ‘historical’ outcomes. The primary endpoint is N0 nodal control rate. In order to consider the treatment regimen worthy of further study the data need to support a N0 control rate no worse than that observed from the historical data. Similar conditions need to be observed for the secondary endpoints of locoregional control rate and 3-year disease-free survival.

N0 nodal control rate is defined as the percent of eligible patients who experience N0 recurrence within the minimum follow-up period of 3 years. Locoregional control rate is defined as the percent of eligible patients who experience local and/or regional failure within the minimum follow-up period of 3 years. The N0 neck represents lymph node regions of the neck that were not clinically or radiographically determined to be pathologically involved with metastatic disease to regional lymph nodes at initial presentation. N0 recurrence = failure in the N0 neck region. Isolated N0 recurrence = failure in the N0 neck region without failure elsewhere. Local (primary) recurrence = failure at the initial site of disease. Regional (nodal) recurrence = failure in lymph nodes in the neck (includes N0 recurrence). Distant recurrence = metastatic failure. Progression-free survival (PFS) is defined in section 6.2.2.

Safety is determined by frequency and severity of adverse events (AEs) related to treatment, and are classified and graded according to CTCAE version 4. AEs related to swallowing function during and after treatment will be assessed. Other endpoints of interest include locoregional recurrence-free survival, dose to regional organs at risk (OARs compared to if the N0 volumes received 50 Gy), and QOL as measured by subject-reported functional outcome questionnaires that will quantify patient-reported speech and swallowing function [MD Anderson Symptom Inventory – Head & Neck (MDASI-HN), MDADI (MD Anderson Dysphagia Index) and VHI-10 (Voice Handicap Index)].

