### **1.3.5 Post-treatment Surveillance with PET-CT**

Patients with head and neck cancer are often monitored after treatment with PET CT, as it has been shown to be highly sensitive in the detection of persistent and recurrent disease after treatment(50-52). Multiple studies show that an initial negative PET CT obtained 3 months after definitive radiotherapy can have a negative predictive value (NPV) as high as 100% for locoregional recurrence with an average NPV of 95%(50-52). However, sensitivity of PET is slightly lower for distant metastases(51, 52). Most authors recommend follow-up PET CT from 3 to 6 months after completion of treatment because studies have shown higher false-negative PET scans when obtained less than 3 months after treatment(50, 51, 53, 54). Thus, a negative PET scan 3 to 6 months after treatment may have a very high probability of ruling out any locoregional recurrence in patients who receive a lower dose to the N0 neck.

If a locoregional recurrence is going to occur, it is most likely to recur within 1 to 2 years, as nearly 90% of all HNC failures occur within the first 2 years after treatment(36). Yao et al (2005) found that 11/150 (7.3%) HNC

patients treated with IMRT developed locoregional recurrences in a median time of about 5 months (range of 2 to 16 months)(37). Their local recurrence-free survivals at 2 and 3 years were equivalent at 94%, and locoregional recurrence-free survivals at 2 and 3 years were also equivalent at 92%. Eisbruch et al reported a 16% rate of locoregional recurrence at a median time of 8 months (55), while Huang et al (2008) reported 10% developing locoregional recurrences at a median time of 15 months (range of 3 to 43 months)(31). Thus, any patient disease-free at 2 years has a very high likelihood of remaining disease-free. However, data is not available for the recurrence of the N0 volumes in the above studies, and they did not stratify their data according to p16 status, which provides vital prognostic significance. Our p16+ patients had 100% control of the N0 volumes at 3 years after treatment, so any isolated recurrence in the N0 volumes after dose reduction at any time in this current study would be suspicious for an inferior treatment.

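### The N0 go/no-go criterion in 7.1 takes the historical point estimate of 1/60 as comparator with no margin, confidence level or failure limit, and 45 patients cannot support it as worded

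*Combined protocol and SAP*

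**What the plan says.** Section 7.1 names the N0 nodal control rate as the primary endpoint and makes advancement conditional: "the data need to support a N0 control rate no worse than that observed from the historical data". It adds: "Similar conditions need to be observed for the secondary endpoints of locoregional control rate and 3-year disease-free survival".

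Section 7.2 supplies the benchmark from sixty patients treated at the same centre: "For those sixty patients, N0 recurrence occurred in 1/60=1.7% and locoregional failure occurred in 6/60=10" percent, "with the upper limit of a one-sided 95% CI being 7.7% and 19%, respectively". It also sets a sequential probability ratio test (SPRT) for N0 failure, 2% against 8% with nominal errors of 10% and 10%, using only the upper boundary. The printed table stops at 2 or more failures (2-9 participants), 3 or more (10-33) and 4 or more (34-45).

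Section 7.3 plans a point estimate and a confidence interval for N0 control, with no level and no decision rule. For PFS it plans a test of the exponential parameter, 0.0744 against 0.1335.

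On terminology, 7.1 states that "N0 nodal control rate is defined as the percent of eligible patients who experience N0 recurrence within the minimum follow-up period of 3 years". That describes a failure percentage, and the 2% and 8% in 7.2 are likewise labelled control rates. All rates below are failure rates.

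**The concern.** The comparator is the rate observed in 60 patients, treated as a fixed bar although 7.2 itself puts its upper limit at 7.7%. Nothing in the plan turns the requirement that the data support a rate no worse than this into a rule that can be applied to 45 patients.

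The criterion decides whether the reduced-dose regimen goes forward. If 1, 2 or 3 N0 failures are seen, the same data can be called success or failure, and the reading would be chosen after the result is known. Each available reading also has a defect of its own: it either turns away regimens as good as standard or lets through too many at the plan's own unacceptable rate.

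**Working it through.** **Inputs.** Historical N0 failure 1/60, its upper limit 7.7%, monitoring rates 2% and 8%, the stopping table and n = 45 eligible patients, all from 7.2. X is the number of N0 failures among 45 with complete 3-year data, taken as binomial(45, p). Confidence limits are exact (Clopper-Pearson).

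**1. The plan's own figures.** The one-sided 95% upper limits are 7.66% for 1/60 and 18.8% for 6/60, agreeing with the stated 7.7% and 19%. For the SPRT:
- Denominator: ln[0.08×0.98/(0.02×0.92)] = 1.449.
- Slope: ln(0.98/0.92)/1.449 = 0.0436 (stated 0.043).
- Intercept: ln(0.9/0.1)/1.449 = 1.516 (as stated).

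**2. Point comparison (observed rate no higher than 1/60).** 1/45 = 2.22% exceeds 1.67%, so only 0/45 passes. At p = 1/60, P(X = 0) = (59/60)^45 = 0.469, so an equivalent regimen is rejected 53% of the time. At p = 2%, P(X = 0) = 0.98^45 = 0.403, so rejection is 60%.

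**3. Exclusion (upper limit at or below 1.67%).** The best possible result is 0/45. Its one-sided 95% upper limit is 1 − 0.05^(1/45) = 6.4%, and its 90% limit is 5.0%. No result passes, so rejection is 100%.

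**4. Compatibility (lower limit of the two-sided interval at or below 1.67%).**

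| Failures | 90% lower limit | 95% lower limit |
|---|---|---|
| 1/45 | 0.1% | 0.06% |
| 2/45 | 0.8% | 0.5% |
| 3/45 | 1.8% | 1.4% |
| 4/45 | 3.1% | 2.5% |

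The 90% interval lets up to 2 failures pass and the 95% interval up to 3. At p = 1/60, P(X ≥ 3) = 3.9% and P(X ≥ 4) = 0.7%, which are the rejection rates.

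**5. The same compatibility readings at 8%.** P(X ≤ 2) = 29% and P(X ≤ 3) = 51%. Applying the printed stopping table after each patient in sequence, a regimen at 8% is stopped 58.7% of the time and so completes 41% of the time.

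**6. Pass probabilities of a fixed count, before any early stopping.**

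| Rule | p = 1/60 | p = 2% | p = 8% |
|---|---|---|---|
| At most 1/45 | 83% | 77% | 12% |
| At most 2/45 | 96% | 94% | 29% |

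The at-most-1 row is unaffected by the stopping table, whose lowest boundary is 2. With the table applied, the at-most-2 row becomes 95.6%, 93.3% and 28.5%.

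**The case against.** The strongest reply is that the plan's own usage points to a lenient reading. Section 7.3 uses the language of data supporting a hypothesis in a testing sense. Its null of 0.0744 is −ln(0.80)/3, the historical PFS, so for PFS the historical rate is abandoned only on evidence of a worse outcome. The SPRT likewise tolerates up to 3 failures at 34-45 participants. The study is described as a pilot, its primary objective is estimation, and 1.4 leaves equivalence to later, larger studies.

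Much of this stands, and it rules out three stronger inferences.

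- A reader might infer that a single failure in 45 fails the criterion. The documents never say so, and the 53% belongs to one reading only. It is also close to half: it drops below 50% if the true rate is under 1.53%, or at 1/60 if 41 or fewer patients are evaluable.
- A reader might treat the N0, locoregional and PFS conditions as three point comparisons and compound them. The plan gives no such cut-offs. PFS has its own one-sided 10% test; on the exact binomial fallback, rejection begins at 13 or more events of 45 (level 0.0995). For locoregional control 7.2 plans only an interval.
- A reader might see a contradiction in 1.3.5, which says "Our p16+ patients had 100% control of the N0 volumes at 3 years after treatment". That section draws on the published series, whereas 7.2 says its sixty patients were updated since publication. The warning in 1.3.5 also concerns isolated recurrence, which 7.1 defines separately, and 7.2 does not say whether the one recurrence was isolated. Both figures can be right.

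The reply does not supply a rule for the primary endpoint. The SPRT is described as protection against excessive failures, and not crossing its boundary is nowhere defined as success. If the compatibility reading is intended, its pass rate at 8% needs to be stated and accepted in advance.

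**Conclusion.** The concern holds in this form: the primary criterion is not operational, and its literal claim is beyond 45 patients. Depending on the reading, a regimen with a true failure rate of 1/60 is rejected 0.7%, 4%, 53% or 100% of the time. The two readings that spare it pass a regimen at 8% between 29% and 51% of the time before early stopping; for the 3-failure version the figure is 41% once the printed table is applied.

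These figures assume independent patients, 45 eligible with complete 3-year N0 status, exact intervals and, where the table is used, sequential application patient by patient. The finding that no rule is stated depends on none of these. Because the gap governs the conclusion on the primary endpoint, it should be closed before outcome data are reviewed.

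**What to change.** Replace the sentence in 7.1 with a maximum N0 failure count among 45 eligible patients, tied to the 2% and 8% rates in 7.2, and print its pass probabilities. At most 1/45 is one option: 83%, 77% and 12% at 1/60, 2% and 8%. At most 2/45 is another: 96%, 94% and 29%, or slightly lower once the stopping table is applied. The choice is a trade-off: the first rejects 23% of regimens at 2%, while the second passes 29% at 8%. Neither meets the nominal 10% and 10% of the SPRT on both sides. If at most 1 is chosen, no separate clause about the stopping boundary is needed.

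In the same edit:
- State that the study cannot show a rate no worse than historical, and can at most make a rate near 8% unlikely. The stricter count serves that claim better; even so, 1/45 has a 90% interval reaching 10.1%.
- Tie the PFS condition to the one-sided 10% test already in 7.2 and 7.3.
- Report locoregional control with its interval beside the historical one, as supportive.
- Replace disease-free survival in 7.1 with PFS, the endpoint defined in 6.2.2 and benchmarked in 7.2.
- Leave the 100% in 1.3.5 as it is; at most, add a note that the updated series has 1/60.

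The cost is protocol wording only, with no added patients or procedures. The downside is a weaker claim.
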